## Schematic of Study Design

### Phase 1:

#### Prior to Enrollment

N=30 clinicians: Obtain informed consent from clinic directors. Conduct initial informational and question/answer sessions.

Assess provider workflows via in-clinic observations of providers

#### Workflow Analysis

Structured workgroup review, presentation of specific tool suite use-cases, group discussion of clinic workflow, creation of optimized visualizations and recommendations by research team, facilitated group adaptation session, revision of recommendations by research team with modified workflow diagrams, discussion of candidate workflows.

#### Tool Suite Optimization

**Final Assessments**  
Discussion of needs for additional dDPP tool adaptation.

#### Tool Suite Rating and Debrief

### Phase 2:

#### For Providers:

- Total n: 40, Obtain verbal consent from provider
- Conduct interviews regarding the provider-facing EHR dashboard

[figure not shown]
#### Workflow Observations & Analysis

Study team to assess provider workflows via short interviews about current scope of work

CONFIDENTIAL

This material is the property of the NYU School of Medicine and NYU Langone Health. Do not disclose or use except as authorized in writing by the study sponsor Behavioral Intervention Template Version: 11 January 2019

CONFIDENTIAL

This material is the property of the NYU School of Medicine and NYU Langone Health. Do not disclose or use except as authorized in writing by the study sponsor Behavioral Intervention Template Version: 11 January 2019

For Patients:

Prior to Enrollment  
Day 0

Total 40: Screen potential participants by inclusion and exclusion criteria; obtain history, document, Send recruitment message via mychart or email for interest in research study.

Visit 1  
Day 1

Obtain informed consent, collect Initial assessments (demographics, behavioral questionnaires: eHEALS, ATMS time management, WHOQL-BREF, GSE, Digital ID) Onboard patient into Noom and fitbit or ihealth accounts, and provide overview

Visit 2  
Week 1 - 2

Follow up interview regarding week 1 experience  
Technical trouble shooting as needed

**Visit 3, 4, 5**  
Month 1,  
Month 3  
Month 6

Follow-up assessments  
(COMB questionnaires and follow up regarding experience in research study regarding text messages, Noom experience, and patient-provider relationship)

Visit 6  
Month 12

Follow-up assessments  
(COMB questionnaires and follow up regarding experience in research study regarding text messages, Noom experience, and patient-provider relationship)

Visit 7  
Month 18

**Final Assessments**  
Follow up questionnaires (COMB, experience after Noom)

Phase 3:

For Patients:

[figure not shown]
Prior to Enrollment  
Day 0

Total 432: Screen potential participants by inclusion and exclusion criteria; obtain history, document, Send recruitment message via mychart, email or phone call for interest in research stud.

CONFIDENTIAL

[figure not shown]
This material is the property of the NYU School of Medicine and NYU Langone Health. Do not disclose or use except as authorized in writing by the study sponsor Behavioral Intervention Template Version: 11 January 2019

Phase 3:

For Providers:

- Total n: 20-40, Obtain verbal consent from provider
- Survey regarding the provider-facing EHR dashboard

CONFIDENTIAL

This material is the property of the NYU School of Medicine and NYU Langone Health. Do not disclose or use except as authorized in writing by the study sponsor Behavioral Intervention Template Version: 11 January 2019

## 2 Introduction, Background Information and Scientific Rationale

### 2.1 Background Information and Relevant Literature

Digital health interventions have become ubiquitous, promising to disrupt standards of care across many health conditions. Their reach, enabled by the dissemination of high speed internet connections, now extends to most of the U.S. population, crossing geographical, socio-demographic and logistical barriers. Despite this rapid expansion, only recently have clinically effective, reimbursable digital interventions become widely available, particularly for lifestyle-sensitive conditions such as diabetes. This expansion has led to growing interest in integrating the patient-generated digital data from these interventions in a useful, streamlined fashion into routine care for chronic conditions. However, there remains a lack of evidence about how to combine and effectively leverage widely available tools in the EHR to use these data to improve

CONFIDENTIAL

This material is the property of the NYU School of Medicine and NYU Langone Health. Do not disclose or use except as authorized in writing by the study sponsor Behavioral Intervention Template Version: 11 January 2019

clinician-patient interactions and patients' engagement in their own self-management and health outcomes.

The Diabetes Prevention Program (DPP) and several other studies have established that DM2 is largely preventable through behavior changes. In the DPP, participants randomized to the comprehensive lifestyle intervention experienced a 58% reduction in diabetes incidence over 3 years and 34% over 10 years.

## **2.2 Rationale**

The proposed project will fill a critical gap in the evidence base and answer an important question: how can EHR tools work together to enhance patient engagement with dDPPs by amplifying providers' ability to support patients' self-management of their health in a meaningful, personalized and timely manner? The proposal is highly innovative in three ways:

1. It will create a **new evidence base** to guide the use of widely available EHR tools for the meaningful integration and display of dDPP patient-generated data, and create a framework for future integrations of other digital behavior change interventions.
2. It will leverage the EHR and its ability to **automate feedback loops** through PAMS to create an innovative process to facilitate provider involvement in their patients' use of the dDPP, **amplifying providers' motivational impact** on patient engagement.
3. It will be evaluated and optimized using **evidence-based implementation frameworks** that will guide assessment of the acceptability, adoption, cost, and sustainability of the tool, an often ignored but key component of evaluating the integration of new care processes. This will provide comprehensive implementation measures, formative and summative, and enable a rigorous understanding of barriers and facilitators to implementing dDPP-EHR tools.

This study aims to adapt a previously developed suite of digital patient monitoring and engagement tools that will integrate patient dDPP data into the EHR workflow. End-user testing is critical in the development of a tool that is optimally effective and usable in practice. We will implement a user-centered design process to adapt the dDPP tool suite to the EHR by iteratively refining and testing and evaluating the acceptability and usability of the enhanced tool suite.

This study will partner with an existing third-party dDPP vendor ("Noom"), which provides a comprehensive digital diabetes prevention curriculum, plus individualized coaching, goal setting, and social groups to help prevent the progression to diabetes in patients who are at risk. This application ("app") is based on the evidence-based CDC DPP program, and will serve as the platform for the delivery of diabetes prevention education content for our patients.

The development and optimization process for the adapted dDPP tool suite involves a series of linked steps that we have successfully used to adapt similar tools in previous studies. The process for phase 1, outlined in completion in IRB-approved study 19-A1-00-1000729, includes a workflow analysis and tool optimization. We will conduct a workflow analysis adapted from the AHRQ recommendations on workflow assessments in five clinics in which these observations will involve seeing the clinician in their usual setting and documentation of existing workflow. We will then use the tool optimization through a structured workgroup review process with relevant clinicians, clinical decision support developers, and the research team.

CONFIDENTIAL

This material is the property of the NYU School of Medicine and NYU Langone Health. Do not disclose or use except as authorized in writing by the study sponsor Behavioral Intervention Template Version: 11 January 2019

Phase 2 of the study will be to pilot the adapted dDPP tool suite in NYU Langone clinics to account for real-world settings (i.e. provider/patient interaction with the updated tool). Early formative observations/short interviews, included in the appendices, will be conducted with care teams, particularly the provider, at each pilot clinic once sufficient patients from that site have enrolled in the dDPP to allow interaction with the new interface tool. This phase of testing will further examine impacts on workflow, usability issues, and potentially lead to additional refinements.

Once the phase 2 intervention has been tested and refined in the NYU Langone clinics, phase 3 of the study will be to recruit practices and patients for the full-scale clinical trial. The intervention will be rolled out to additional sites in a randomized control trial. Patients in the intervention group will receive the dDPP and their providers will have access to the adapted dDPP-EHR tool suite from the previous two phases, while the control patients will only receive the dDPP via mobile application (not integrated into the EHR). The overall outcomes of this phase will be both clinical (i.e. weight reduction, physical activity, HbA1C levels) and engagement-related (i.e. patient engagement and perceived provider involvement).

## **2.3 Potential Risks & Benefits**

### **2.3.1 Known Potential Risks**

Patient participants will be using their MyChart mobile health applications and receiving text messages. General risks of using mobile applications (“apps”) include the possibility of personal or financial information being (un)intentionally disseminated to parties outside of the app vendor. To address this, the mobile app partner (“Noom”) adheres to standard industry protocols for data safety and monitoring. Participants may also feel frustrated when sharing their opinions and completing questionnaires, in which case they will be instructed to skip as they see fit. All risks and benefits of participation will be explained to participants and included in the verbal consents and key information sheet. The primary risk to NYULH employee subjects would be anxiety about being observed or interviewed. We will reassure employee subjects that their responses will not be communicated to supervisors and will not be part of any performance evaluation.

### **2.3.2 Known Potential Benefits**

All patient participants will receive a free 1 year subscription to the dDPP mobile health application, which they can use as they please. In terms of long-term benefits, prior similar research have helped participants improve their health maintenance, and relationship with their providers, by implementing the suggested health behavior changes using dDPP, and increased provider input in the healthcare decisions.

## **3 Objectives and Purpose**

### **3.1 Primary Objective**

Primary Objective: To observe percent change in weight

### **3.2 Secondary Objectives (if applicable)**

Secondary Objective: To observe any change in clinical outcomes (steps per day, hemoglobin A1c levels) and to asses impact of engagement messaging and user engagement scores

CONFIDENTIAL

This material is the property of the NYU School of Medicine and NYU Langone Health. Do not disclose or use except as authorized in writing by the study sponsor Behavioral Intervention Template Version: 11 January 2019

## 4 Study Design and Endpoints

### 4.1 Description of Study Design

This study has 3 phases and is a mixed methods study.

Phase 1: Quality improvement study (Refer to prior approved study 19-A1-00-1000729 in appendices)

Phase 2: Pilot study with 40 NYU patients across NYU Langone Health sites. This is an observational study to understand and assess the usability of workflows for both patients and providers, and adapt as needed

Phase 3: Randomized control trial with 3 arms, across FGP sites in NYU Langone Health. Both control arms and two intervention arms will receive the dDPP app. The intervention arms will receive messages through PAMS based on their engagement levels in the dDPP application.

The intervention arms receive the same group of text messages with one group having the choice to select the time of day for the text messages and whether they would like a reminder to log into Noom on a daily, weekly, biweekly or month cadence.

### 4.2 Study Endpoints

#### 4.2.1 Primary Study Endpoints

Primary endpoint: weight (lb)

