#### 10.4.2 Analysis of the Primary Efficacy Endpoint(s)

The table below outlines the study's main outcomes. Whenever possible, outcomes ascertained via automated or technology-facilitated objective approaches are used to enhance the pragmatic approach and minimize provider and patient burden; while weight and activity data will be collected more frequently (and be viewable to intervention patients and providers), 6- and 12- month assessments will be used to evaluate impact. To ensure data endpoint capture for weight and physical activity at 6 and 12 months, the study team will conduct outreach and troubleshoot with patients missing data at any of these intervals.

Construct	Measure	Data Source	Collected at (months)
Clinical outcomes	Weight reduction (kg)	Noom via wireless scale and survey, EHR	Baseline, 3, 6, 9, 12
	Physical activity (steps/day)	Noom via wireless pedometer	Baseline, 6, 12
	Hemoglobin A1C (%)	HbA1C home test kit and survey, EHR	Baseline, 6, 12
Engagement outcomes	Patient engagement (# dDPP logins) (# dDPP lessons completed)	Noom	6, 12
	Perceived provider involvement with dDPP progress	Patient portal 1-item survey	
Patient characteristics	Demographics, social determinants, and other baseline descriptive data	EHR	Baseline, 12

Change in body weight, a repeatedly measured continuous variable, will be our primary weight-based outcome. Secondarily, we will assess achievement of a 7% weight loss (the DPP weight goal), a binary outcome. Weight will be collected from the bluetooth linked wireless weight scale (Fitbit Aria or iHealth Fit/Nexus) that automatically reports weigh-ins to the Noom server. Mean steps per day, a repeatedly measured continuous variable, will be assessed using Fitbit or iHealth accelerometers integrated into the Noom platform. This objective device has been well-validated for the measurement of steps and found to be acceptable by study participants. HbA1C, the most common test used for prediabetes monitoring, will be assessed as a secondary outcome via HbA1C testing performed at home. HbA1C will be collected at baseline, 6 and 12 months. Patients will be sent a HbA1C testing kit upon enrollment, and prompted by

CONFIDENTIAL

This material is the property of the NYU School of Medicine and NYU Langone Health. Do not disclose or use except as authorized in writing by the study sponsor Behavioral Intervention Template Version: 11 January 2019

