the study team at each time point to complete testing. HbA1C testing kits have been shown in prior studies to be safe and equivalent to laboratory testing, and are increasingly used in pragmatic digital studies to avoid unnecessary burden on participants.

For continuous outcomes including weight reduction, mean steps per day, and reduction in HbA1C level, we will use generalized estimating equations (GEE) to compare treatment arms with time and intervention as a fixed effect and practice as a random effect, to adjust for clustering of patients within practices. Participant demographic characteristics including age, gender, race/ethnicity and other potential confounders determined as a priori will be controlled for in GEE. We will also collect patient characteristics, such as demographic information, social determinants, and other baseline descriptive data, from the EHR. For the second outcome of 7% weight-loss achievement, we will use a similar GEE model with a logit link function. We will report the estimated effect of intervention and its associated 95% confidence interval calculated by using the robust variance estimator. We will also report the intra-cluster correlation and time effect from the fitted model.

Missing data frequently occur in pragmatic clinical trials with long follow-up. To supplement missing HbA1C and weight data from patients, we will conduct EHR data extractions. Our data analyst will run a query based on the appropriate time windows per patient to pull values and dates for HbA1C and weight, respectively. Standard GEE will be unbiased only if data are missing completely at random (MCAR), which rarely occurs in practice. Thus, we will apply weighted GEE to accommodate the more realistic missing at random (MAR) assumption. Due to the large number of clinics, providers, and patients, we expect balance by study arm over patient, provider, and clinic characteristics. In case of imbalance, however, we will investigate propensity score weighting to adjust the observed differences.

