#### **10.4.8 Additional Sub-Group Analyses**

No sub-group analyses are planned.

The primary endpoint of weight loss will be analyzed using a two-sided Type I error rate of 0.05. Other outcomes are considered secondary outcomes and no adjustment is required.

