#### **10.4.9 Multiple Comparison/Multiplicity**

We will start with univariate analysis of associations of intervention with each clinical and engagement outcome measured at 6 and 12 months. This enables us to see if effect of intervention clinical and engagement outcomes changes with time. If so, we may consider including interaction terms between intervention and time in GEE. We will also examine potential heterogeneity of intervention effect by participant baseline demographics and clinical measures by running stratified GEE. Other potential analyses of interest could be the analysis of association between changes in engagement and changes in clinical outcomes over time.

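### The trial is sized on a 12-month difference in kg, but the primary GEE as written estimates a 6- and 12-month average, and the primary weight variable is defined in three ways

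*Combined protocol and SAP*

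**What the plan says.** **The variable.** Section 3.1 reads "Primary Objective: To observe percent change in weight". Section 4.2.1, like the endpoint row of the Protocol Summary, reads "Primary endpoint: weight (lb", with no change measure and no time point. Section 10.4.2 states "Change in body weight, a repeatedly measured continuous variable, will be our primary weight-based outcome", and its table lists weight reduction in kg. The objective in the Protocol Summary also speaks of change in weight.

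**The time point.** Section 10.5 assumes 1-year losses of 4.5 and 2.5 kg, a difference of 2 kg, with an SD of 5 kg at 1 year. Section 10.4.2 says of the 6- and 12-month visits that these "month assessments will be used to evaluate impact" and ranks neither first. Section 10.4.8 adds "The primary endpoint of weight loss will be analyzed using a two-sided Type I error rate of 0.05", again without a time point.

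**The model.** Section 10.4.2 uses GEE "to compare treatment arms with time and intervention as a fixed effect and practice as a random effect" and reports a single intervention effect. On covariates it says "Participant demographic characteristics including age, gender, race/ethnicity and other potential confounders determined as a priori will be controlled for in GEE". Baseline weight is not named. Sections 10.4.9 and 10.4.10 first look at each outcome at 6 and 12 months to see whether the effect changes with time, and then say "If so, we may consider including interaction terms between intervention and time in GEE".

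**The concern.** With main effects for arm and time only, the arm coefficient is one number shared by all visits in the model. With 6- and 12-month rows it is the average of the two visit differences. That is a legitimate quantity, but it is not the one the trial was sized for, and the plan does not declare it as the target. If the benefit is still growing at month 6, the reported effect falls short of the 12-month benefit.

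The interaction term is considered only after the visit-specific effects have been examined. Nothing says which estimate is primary once it is added, so the choice between a visit average and a 12-month contrast can be made with the results in view.

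The scale matters less but still needs settling. Pounds against kilograms is only a unit conversion. Weight level, absolute change and percent change are different variables: 2 kg is 2.5% of an 80 kg person and 1.8% of a 110 kg person (illustrative weights).

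**Working it through.** **Inputs from the plan.** 12-month difference 2 kg, SD 5 kg, two-sided alpha 0.05 (10.5); 432 patients randomized 1:2 (10.4.1), with 144 in control (Protocol Summary).

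**Assumptions, not in the plan.** Intervention arms pooled (144 vs 288) or one arm against control (144 vs 144); 6-month SD s6 of 4 to 5 kg; correlation ρ between 6- and 12-month change of 0.5 to 0.85.

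**Formula.** SE = SD × √(1/n1 + 1/n2); power = Φ(difference/SE − 1.96).

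**1. The plan's own figures.**

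| Patients per arm | Difference | Computed | Stated |
|---|---|---|---|
| 200 | 2 kg | 97.9% | 97% |
| 200 | 1.75 kg | 93.8% | 93% |
| 160 | 2 kg | 94.7% | 94% |

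The figures reproduce, so the powered quantity is the single 12-month contrast in kg.

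**2. The same contrast with 432 patients.** For 144 vs 288, SE = 5 × √(1/144 + 1/288) = 0.510 and power is 97.5%. For 144 vs 144, SE = 0.589 and power is 92.4%.

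**3. What the main-effects model estimates when the 12-month difference is 2 kg.**
- Linear growth (1 kg at month 6): (1 + 2)/2 = 1.5 kg.
- Full effect by month 6: (2 + 2)/2 = 2.0 kg.
- The table in 10.4.2 also collects weight at months 3 and 9. If those rows entered, linear growth would give (0.5 + 1 + 1.5 + 2)/4 = 1.25 kg.

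Simulated trials (exchangeable GEE, 400 per setting, linear growth, 144 vs 288) gave arm coefficients of 1.48 and 1.51 kg without the interaction. With the interaction and baseline weight, the 12-month contrast was 1.96 and 2.01 kg.

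**4. Power of the visit average.** SD_avg = √((s6² + 25 + 2ρ·s6·5)/4).

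| s6, ρ | SD_avg | 144 vs 288: linear / full by month 6 | 144 vs 144: linear / full by month 6 |
|---|---|---|---|
| 4, 0.5 | 3.905 | 96.4% / 99.9% | 90.3% / 99.1% |
| 4, 0.85 | 4.330 | 92.4% / 99.5% | 83.6% / 97.5% |
| 5, 0.5 | 4.330 | 92.4% / 99.5% | 83.6% / 97.5% |
| 5, 0.85 | 4.809 | 86.4% / 98.3% | 75.4% / 94.2% |

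**5. Type I error if the estimate is chosen after the data.** These figures use the bivariate normal distribution of the 6- and 12-month z values under no effect, with the same s6 and ρ. The decision rules are illustrations; the plan states none.
- An interaction test at 5% decides between visit average and 12-month contrast: 5.2 to 6.0%.
- Either the visit average or the 12-month contrast may be claimed: 6.1 to 7.3%.
- Significance at either 6 or 12 months counts: 7.5 to 9.1%.

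**6. Baseline weight as covariate.** Assume a between-person SD S of 15 to 22 kg, equal at both visits. Then r = 1 − 25/(2S²) and the residual SD is S√(1 − r²), which is 4.93 kg (S = 15) to 4.97 kg (S = 22). Power for 144 vs 288 is 97.8 to 97.6%, against 97.5% without it.

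**The case against.** The strongest reply is that the plan is under-specified rather than wrong. Section 10.4.2 describes its model in prose and does not forbid an interaction, and 10.4.9 and 10.4.10 provide for visit-specific analyses. The trial is described as lasting one year and is sized at one year, so month 12 could be read as implied. The interaction wording sits under an exploratory heading and is repeated under multiplicity, perhaps by a copying slip; nothing says it replaces the primary estimate. A visit average is a valid target, and the shortfall vanishes if the effect is full by month 6. The type I figures rest on rules the plan never states, and the rule closest to its text gives only 5.2 to 6.0%.

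Much of this is fair on size. The shortfall is conditional on the time course, the type I figures are illustrative, and the baseline-weight gain is small. It does not remove the point. Section 10.4.2 expressly uses both visits and reports one intervention effect, and no section names the 12-month contrast as primary. The trial's length does not choose between visits. The plan gives no 6-month effect, so equality with the sizing target cannot be assumed.

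**Conclusion.** The concern holds. Section 10 largely settles the variable as absolute change in kg, but 3.1 and 4.2.1 do not match it. The time point is not settled: the powered quantity is the 12-month difference, and the model as written targets the average of 6 and 12 months. Under linear growth a true 2 kg becomes 1.5 kg, a quarter less; if the full effect is present by month 6, nothing is lost.

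The powers of the visit average and the type I error ranges depend on the assumed 6-month SD and correlation. The 144 vs 288 figures also depend on pooling the intervention arms. The 12-month kg contrast has adequate power, so this should be corrected, but it does not threaten the trial's viability.

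**What to change.** 1. In the Protocol Summary, 3.1 and 4.2.1, state the primary endpoint as change in body weight (kg) from baseline to 12 months. Keep percent change as supportive.
2. In 10.4.2, fit the primary GEE to the follow-up rows with arm, time, arm-by-time and baseline weight as prespecified terms. List the visits that enter the model. Name the 12-month contrast as the primary estimate and the 6-month contrast as secondary.
3. Keep arm-by-time whatever the visit-specific results show. Bring the parallel model wording in 10.4.1 and the conditional wording in 10.4.9 and 10.4.10 into line.

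**Cost.** Text changes only; no new patients or measurements. Under the assumptions above, power of the 12-month contrast compares with the visit average as follows:

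| Comparison | Loss if full by month 6 | Gain if linear |
|---|---|---|
| 144 vs 288 | about 1 to 2 points | about 1 to 11 points |
| 144 vs 144 | about 2 to 7 points | about 2 to 17 points |

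The 12-month contrast also leans more on the 12-month visit, so missing 12-month weights matter more.
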